3.2.1.1.6 Overall survival [OS]

Overall survival is defined as the time from randomisation (patients recruited under CSP version 7.0) or the start of treatment (patients recruited prior to CSP version 7.0) until death due to any cause (i.e. date of death or censoring – date of first dose + 1). Any patient not known to have died at the time of analysis will be censored based on the last recorded date on which the patient was known to be alive.

Patients will be contacted for survival follow-up every 12 weeks. In addition to survival data, information regarding any subsequent anti-cancer treatment will also be collected. The impact of cross over on OS may need to be assessed.

Patients should be contacted in the week after data cut-off [DCO] for each analysis to establish survival status, and if patients are confirmed to be alive or if the death date is after the DCO date these patients will be censored at the date of DCO. The status of ongoing, withdrawn (from the study) and “lost to follow-up” at the time of the final OS analysis should be obtained by the site personnel by checking the patient’s notes, hospital records, contacting the patient’s general practitioner and checking publicly-available death registries. In the event that the patient has actively withdrawn consent to the processing of their personal data, the vital status of the patient can be obtained by site personnel from publicly available resources where it is possible to do so under applicable local laws.

It may be necessary to use all relevant eCRF fields to determine the last recorded date on which the patient was known to be alive for those patients still on treatment. The last date for each individual patient is defined as the latest among the following dates recorded on the case report forms [CRFs]:

- AE start and stop dates
- Admission and discharge dates of hospitalization
- Study treatment date
- End of treatment date
- Laboratory test dates
- Date of vital signs
- Disease assessment dates on RECIST CRF
- Start and stop dates of alternative subsequent anticancer treatment (including radiotherapy)
- Date last known alive on survival status CRF
- End of study date

3.2.2 Safety Outcome Variables

The safety outcome variables which address the safety and tolerability of savolitinib in combination with

osimertinib are described in Section 8.2 of the Clinical Study Protocol.

3.2.2.1 Duration of Exposure

Duration of exposure will be summarised for savolitinib and osimertinib separately and is defined as:

1. Total treatment duration (days) = (min(last dose date where dose > 0 in Study Treatment Log, date of death, date of data cut-off) – date of first dose +1).
2. Actual treatment duration (days) = total treatment duration, excluding dose interruptions and any planned no dose periods.

Where total and actual treatment durations are presented in months, the following conversion should be made:

$$\text{Treatment duration (months)} = \text{Treatment duration (days)} / (365.25/12).$$

Exposure will also be measured by the number of cycles started. A cycle corresponds to a period of 28 days. A cycle will be counted if treatment is started even if the full dose is not delivered.

Dose modifications

Study Treatment Log records dosing details for each dosing day. Dose interruptions and reductions will be counted for savolitinib and osimertinib separately.

Dose interruption is defined as the total number of interruptions recorded in treatment logs excluding any planned interruptions in accordance with the protocol. Dose reduction is defined as the total number of reductions recorded in treatment logs. Dose modification is defined as the total number of reductions or interruptions recorded in treatment logs. Dose interruption, dose reduction and dose modification will be calculated for savolitinib and osimertinib in the first 6 weeks and for the whole treatment period.

Missed and forgotten doses should be recorded on the dose module as a dose interruption with the reason recorded as “Patient forgot to take dose”. These missed or forgotten doses will not be included as dose interruptions in the summary tables, but the information will appear in the listing for dosing. However, these missed and forgotten doses will be considered in the derivation of actual exposure.

If a patient permanently discontinues study treatment during a dose interruption, then the date of last administration of study medication will be used in the programming.

3.2.2.2 Dose Intensity

Dose intensity of savolitinib and osimertinib will be addressed by considering relative dose intensity [RDI].

RDI is the percentage of the actual dose delivered relative to the intended dose through to treatment discontinuation. RDI will be defined as follows:

$$\text{RDI} = 100\% * d/D, \text{ where } d \text{ is the actual cumulative dose delivered up to the actual last day of dosing and } D \text{ is the intended cumulative dose up to the actual last day of dosing. } D \text{ is the total}$$

dose that would be delivered if there were no modification to dose or schedule.

Where appropriate, the intended dose [D] will reflect the dose reassignment from 600 mg to 300 mg of savolitinib. Therefore, if a patient, who started with savolitinib 600 mg, subsequently decides to switch to savolitinib 300 mg, the switching date should be used to adjust the intended dose.

3.2.2.3 Adverse Events

An AE is defined as the development of any untoward medical occurrence in a patient or clinical study patient administered a medicinal product, and which does not necessarily have a causal relationship with this treatment. The term AE is used to include both serious and non-serious AEs and can include a deterioration of a pre-existing medical occurrence.

AEs and Serious adverse events [SAEs] will be collected from the time of signing of the main study Informed consent form [ICF] throughout the treatment period and including the follow-up period. The follow-up period is defined as 28+7 days after study treatment is discontinued.

AEs will be defined as treatment emergent adverse events [TEAEs] if they have an onset or worsen (by investigator report of a change in severity) during the study treatment period (defined from date of first dose of any study treatment to date of last dose of any study treatment) or safety follow-up period (28 days [+7 days] after last dose of study treatment). Any events in this period that occur after a patient has received further therapy for cancer (following discontinuation of study treatments) will be flagged in the data listings. AEs with a missing start time which occur on the same day as first IP administration will be reported as on-treatment.

The Medical Dictionary for Regulatory Activities [MedDRA] (version 21.0 or later) will be used to code the AEs. AEs will be graded according to the National Cancer Institute Common Terminology Criteria for AEs [CTCAE Version 5 or later].

Other significant adverse events [OAE]

During the evaluation of the AE data, an AstraZeneca medically qualified expert will review the list of AEs that were not reported as SAEs and AEs leading to discontinuation. Based on the expert's judgement, significant AEs of particular clinical importance may, after consultation with the Global Patient Safety Physician, be considered other significant adverse events and reported as such in the clinical study report. A similar review of laboratory/vital signs/ Electrocardiogram [ECG] data and other safety assessments will be performed for identification of other significant adverse events. This review will take place at least prior to primary and final analyses and prior to database lock, and any AEs identified will be fully documented in meeting minutes.

Examples of these could be marked haematological and other laboratory abnormalities, and certain events that lead to intervention (other than those already classified as serious), dose reduction or significant additional treatment.

Potential Hy's Law

Potential Hy's Law is defined as aspartate aminotransferase [AST] or alanine aminotransferase [ALT] $\geq 3 \times$ upper limit of normal [ULN] together with total bilirubin [TBL] $\geq 2 \times$ ULN at any point during the study following the start of study medication irrespective of an increase in Alkaline Phosphatase [ALP].

The elevation in transaminases must precede or be coincident with (ie, on the same day) the elevation in TBL, but there is no specified time frame within which the elevations in transaminases and TBL must occur.

Adverse events of special interest [AESI]

AESIs represent pre-specified risks that are considered to be of importance to a clinical development program. Other categories may be added as necessary or existing terms may be merged. AESIs have been identified as a list of categories provided by the patient safety team. An AstraZeneca medically qualified expert after consultation with the Global Patient Safety Physician has reviewed the AEs of interest and identified which higher-level terms and which preferred terms contribute to each AESI.

AstraZeneca medically qualified expert together with the Global Patient Safety Physician may review and update the list of the identified AESI prior to database lock to ensure any further terms not already included are captured within the categories. This review may be considered prior to planned interim, primary and final analyses.

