Examples of these could be marked haematological and other laboratory abnormalities, and certain events that lead to intervention (other than those already classified as serious), dose reduction or significant additional treatment. Tables and figures for potential Hy's Law cases will be produced.

Any AE occurring within the defined 28-day follow-up period after discontinuation of study drug will be included in the AE summaries. AEs occurring after the 28-day follow-up period after discontinuation of study drug or after starting subsequent anti-cancer therapy will be listed separately, but not included in the summaries.

Duration of exposure will be summarised. The number and percentage of patients with at least 1 dose interruption/dose delay and at least 1 dose reduction will also be summarised separately for the first 6 weeks and at any time.

Haematology, clinical chemistry, coagulation, urinalysis, vital signs and ECG data will be listed individually by patient and suitably summarised. For all laboratory variables, which are included in the current version of CTCAE, the CTCAE grade will be calculated.

Details of any deaths will be listed for all patients.

Graphical presentations of safety data will be prepared as is deemed appropriate.

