3.2.2.4 Prior/Concomitant/Post-treatment Medications

Medications will be classified as prior or concomitant (but not both) according to its start/stop date. Prior medication is defined as any medication with a stop date prior to the first dose of study treatment (exclusive). Concomitant medication is defined as any medication with a stop date on or after the first dose of study treatment. Concomitant medication will also include any medication taken prior to or during study treatment that is on-going, including any treatment with a start date within 28+7 days after stopping study treatment.

Subsequent anti-cancer treatment includes therapies with a start date after the last dose of study treatment. Hence, patients starting subsequent anti-cancer treatment will no longer be on the study treatment combination, osimertinib monotherapy, or on savolitinib monotherapy.

The imputation method described in section 3.1.4.2 will be used in case of medication stop date partially missing. Completely missing stop date will not be imputed, and medication will be classified as concomitant.

All medications will be coded according to the World Health Organization Drug Dictionary Enhanced and Herbal Dictionary [WHO-DDE + HD] 2018Mar B3 format, or later version.

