4.2.3.2 Adverse Event

Key guidelines for counting incidence proportions of adverse events are as follows:

- When a patient has the same AE reported multiple times during an analysis period based on SOC and PT, the patient will only be counted once within a level of MedDRA in an AE incidence table.
- When assessing investigator-reported relationship to study drug of the AEs, if an AE changes in causal relationship during an analysis period for a patient, the related event will be chosen. Related AEs will include those reported as related by the investigator and those with a missing relationship. AE with a missing relationship will be presented as related in summary tables but will be presented in the data listing with a missing relationship.
- When summarising intensity of the AEs, if an AE changes in CTCAE grade during an analysis period for a patient, the AE with the maximum CTCAE grade will be chosen. In case the AE term (SOC and PT) is reported more than once, one of them with missing grade, and at least another with non-missing grade, the maximum CTCAE grade will be chosen from the non-missing grade values and the missing grade can be ignored. If all are of missing grade, then the AE severity will be summarised in an additional “Unknown” intensity category.
- When summarising intensity for drug-related AEs, only drug-related AEs will be used in the analysis. If a patient has the same AE reported multiple times during an analysis period for a drug-related AE, the AE with the maximum CTCAE grade will be chosen.

The number and percentage of patients with TEAEs, as classified by SOC and PT, will be summarised for the Safety analysis set:

- Patients with TEAEs and the number of TEAEs
- TEAEs that are causally related to Osimertinib, causally related to Savolitinib, and casually related to either Osimertinib or Savolitinib,
- TEAEs of CTCAE grade ≥ 3
- TEAEs of CTCAE grade ≥ 3 related to Osimertinib or related to Savolitinib
- TEAEs by common frequency ($>5\%$) in descending order
- TEAEs by maximum CTCAE grade
- TEAEs with death outcome
- Non-serious TEAEs that occurred in greater than 5% of patients

- Serious TEAEs
- Serious TEAEs – key patient information
- Serious TEAEs that are assessed by investigator as causally related to Osimertinib, causally related to Savolitinib, and casually related to either Osimertinib or Savolitinib
- TEAEs leading to dose modification of each study treatment

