- TEAEs leading to discontinuation of each study treatment (overall and within the first 6 weeks)
- TEAEs leading to discontinuation of each study treatment - key patient information
- Other significant TEAEs
- Other significant TEAEs leading to discontinuation of each study treatment (overall and within the first 6 weeks)
- TEAEs of special interest
- TEAEs of special interest by CTCAE grade
- TEAEs of special interest leading to discontinuation of each study treatment (overall and within the first 6 weeks)
- Hypersensitivity/anaphylaxis and hepatotoxicity TEAEs of special interest leading to discontinuation of savolitinib (overall and within the first 6, 12 and 24 weeks)

An overall summary table of the number of patients experiencing at least one adverse event will be produced. An overall summary table of the number of AEs will also be provided.

TEAEs in any category, including AESI, TEAEs of CTCAE grade ≥ 3 , deaths, SAEs, TEAEs leading to discontinuation, and other significant TEAEs will be summarised.

AEs occurring prior to first dose of study treatments (i.e., before study Day 1) which subsequently worsen in severity following dosing will be presented in the summary tables. All other AEs occurring prior to first dose of study treatments (i.e., before study Day 1), or after the 35-day follow-up period (28 days allowing for the ± 7 -day window) after discontinuation of study treatments will be listed, but not included in the summaries.

Details of any deaths will be listed for all patients.

All AEs will be listed, and any AEs started on or after a patient took osimertinib after crossing over from 300 mg bid + placebo to 300 mg bid + osimertinib will be flagged.

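### The SAP omits the protocol's exclusion of adverse events that start after subsequent anti-cancer therapy from the AE summaries, and does not declare the change

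*SAP*

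**What the plan says.** **SAP.** Section 3.2.2.3 defines a treatment-emergent AE (TEAE) as one with onset or worsening in the treatment period "or safety follow-up period (28 days [+7 days] after last dose of study treatment". The definition has no cut at the start of new therapy. The section then deals with "Any events in this period that occur after a patient has received further therapy for cancer" by flagging them in the listings.

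Section 4.2.3.2 says: "The number and percentage of patients with TEAEs, as classified by SOC and PT, will be summarised for the Safety analysis set". Its exclusions come at the end. Pre-dose events that worsen after dosing are kept. "All other AEs occurring prior to first dose of study treatments", together with events later than the 35-day follow-up "after discontinuation of study treatments will be listed, but not included in the summaries". Subsequent therapy is not mentioned.

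Section 3.2.2.4 sets the start of next-line treatment: "Subsequent anti-cancer treatment includes therapies with a start date after the last dose of study treatment". It can therefore fall inside the follow-up window.

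**Protocol.** Section 9.4.4 has nearly the same TEAE definition and the same flagging sentence. It then says that AEs within the 28-day follow-up go into the summaries. The next sentence takes out AEs after that follow-up, "or after starting subsequent anti-cancer therapy will be listed separately, but not included in the summaries".

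**Declared changes.** SAP section 6 lists departures from the protocol. This is not among them.

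**The concern.** The two documents give different AE counts for the same patient, and the change is not declared.

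Overlap between the follow-up window and next-line therapy is foreseeable. Protocol 7.1.2 expects patients who permanently stop study treatment to be given local standard of care, and the 28-day contact in 7.1.3 asks about subsequent cancer therapy. The protocol introduction names platinum doublet chemotherapy as the usual choice after an EGFR-TKI for T790M-negative patients who can tolerate it, and lists bone marrow suppression among its toxicities. Protocol 8.3.13 makes haematological events an AE of special interest for osimertinib. A cytopenia caused by next-line chemotherapy could therefore enter the special-interest table as well as the Grade 3 or higher, serious and fatal TEAE tables.

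These tables describe the safety of each dosing regimen. Events that arise under another regimen blur that description, and a flag in a listing does not correct a percentage in a table.

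**Working it through.** The plan states no figure on this point, so the check is a comparison of text. The only arithmetic is the length of the window: 28 + 7 = 35 days after last dose.

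| AE onset | Protocol 9.4.4 | SAP 3.2.2.3 and 4.2.3.2 |
|---|---|---|
| Before first dose, no worsening | Not summarised | Not summarised |
| In the follow-up window, no new therapy yet | Summarised | Summarised |
| In the follow-up window, after new therapy started | Listed separately, not summarised | TEAE, flagged in listings, **summarised** |
| Beyond the follow-up window | Not summarised | Not summarised |

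The third row is where the new-therapy rule separates the two documents.

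**Example.** Take last dose as day 0, chemotherapy from day 10 and a first Grade 3 event on day 25. Since 25 is below both 28 and 35, the event is inside the window under either document. It is after day 10, so the protocol lists it only. The SAP counts the patient in the any-grade and Grade 3 or higher TEAE rows.

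**Does the protocol's exclusion apply inside the window?** The exclusion sentence has two limbs. Events after the follow-up period are covered by the first. If the second limb, on subsequent therapy, did not remove events inside the window, it would add nothing, because events outside it are already removed. The natural reading is that it is an exception to the 28-day inclusion sentence just before it, although the protocol does not say so.

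**What can be said about size.** For a patient-level rate, the rise equals the proportion of patients who start other therapy within 35 days of last dose, multiplied by the proportion of those whose first qualifying event falls between that start and day 35. A patient who already had such an event adds nothing. The documents give neither proportion. The affected interval is at most 35 days per patient, less the gap between last dose and the new therapy.

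**The case against.** **The protocol is not clean either.** Its TEAE definition has no cut at new therapy, its flagging sentence matches the SAP's, and its 28-day inclusion sentence overlaps with the exclusion that follows. The SAP can be said to follow the definition and the inclusion sentence. This stands as a reason to clarify protocol 9.4.4. It does not explain why SAP 4.2.3.2 keeps the protocol's listed-but-not-summarised device and leaves out one of its two limbs. The flagging sentence is common ground; the difference lies in the omission.

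**Inclusion is conservative.** It can raise reported toxicity but not hide it. The safety summaries are descriptive, and the affected events stay identifiable. An exclusion could also drop late study-drug toxicity that appears just after a switch. This is a fair point, and the reason for a supportive inclusive table. It does not justify an undeclared change.

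**Few patients may be affected.** Combination patients may continue past progression (protocol 4.1.1 and 7.1). Placebo-arm patients may cross over to the combination (4.1.2), which is study treatment; SAP 4.2.3.2 flags AEs after crossover separately. Deaths unequivocally due to progression are not reported as SAEs (8.3.12). All of this limits the effect, by an unknown amount.

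**Two stronger readings are tempting.** A reader might infer that next-line toxicity is judged to be caused by study treatment. The documents do not support that: TEAE status is temporal, and the investigator assesses causality for each product (protocol 8.3.5). The related-AE tables are touched only if the investigator calls the event related or leaves the field blank, which SAP 4.2.3.2 counts as related. A reader might also put a figure on the inflation. Guesses of 30% to 50% starting therapy in the window, with 5% to 20% of those having a first Grade 3 or higher event only then, would give 0.30 × 0.05 = 1.5 to 0.50 × 0.20 = 10 percentage points. Nothing in the documents supports those inputs.

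**Conclusion.** The point holds as an undeclared difference between SAP and protocol in how AEs are summarised. It is confined to events with onset or worsening after the start of subsequent therapy and within 28 (+7) days of last dose. For those events the SAP yields a treatment-emergent incidence at least as high as the protocol's. The size cannot be derived from the documents.

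The conclusion rests on reading the protocol's exclusion sentence as an exception to its 28-day inclusion sentence, which is the only reading that gives the subsequent-therapy limb any effect. No efficacy endpoint or hypothesis test is involved. The correction is worth making because the affected rates describe each regimen's safety and the remedy is cheap.

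**What to change.** - **SAP 4.2.3.2, cross-referenced from 3.2.2.3:** keep the TEAE definition. Add that AEs with onset or worsening on or after the start of subsequent anti-cancer therapy are listed but left out of the main summaries. Ending the TEAE period at new therapy would go beyond the protocol, which removes these events from the summaries without redefining them.
- **Radiotherapy:** state whether it counts. SAP 4.2.1 includes post-treatment radiotherapy under subsequent treatment, while the ORR rule in SAP 3.2.1.1.2 does not treat it as subsequent therapy.
- **Supportive table:** give one overall AE table that includes these events, so that late study-drug toxicity after a switch stays visible.
- **Protocol 9.4.4:** say that the exclusion sentence is an exception to the 28-day inclusion sentence.
- **Crossover:** note that moving from savolitinib plus placebo to savolitinib plus osimertinib does not trigger the exclusion.

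If the sponsor prefers to keep these events in the main tables, SAP section 6 should declare and justify it, with a sensitivity summary that removes them.

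The cost is a few sentences, one date condition on events the SAP already flags, and one extra table. The small downside is that late study-drug events after a switch leave the main tables; the supportive table covers that.
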